9.4.6 PLANNED INTERIM ANALYSES

Interim analysis of behavioral outcomes will be conducted at each follow-up point. We do not plan to halt the study based on interim results. If early results indicate strong effects we will continue the study to assess whether the effects persist, and if early results indicate no effects we will continue the study to assess potential delayed effects. In addition, we will continue the study to assess secondary biological outcomes at the final follow-up.

The analysis will be conducted by the PI with data blind-coded by the data manager. The analysis will be reviewed by the co-investigators and the DSMB.

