6.3 MEASURES TO MINIMIZE BIAS: RANDOMIZATION AND BLINDING

The 12 recruitment sites will be pair matched and randomly assigned to a study arm. One of each pair will be assigned to MASLIHAT and the other to the control condition. [name] will create the matched pairs based on site characteristics, and randomization will be determined by the PI using a random number generator. A random number will be generated for each site, and within each matched pair, the site with the smaller number will be assigned to MASLIHAT. To minimize bias during recruitment, site assignments will be masked from project staff engaged in recruitment. The PI will inform the Moscow project coordinator of the site assignment as needed for group scheduling, after the first cohort of participants has been filled for the site. Participants will be informed of their assignment at the time of scheduling the group sessions. [name] will also have access to this information as needed, after recruitment activities are underway. Interviewers will be blinded to site assignment, and the same interview instrument will be used for MASLIHAT and control condition participants. Session facilitators, who may become aware of the recruitment sites from which participants originated, will be instructed during training not to reveal this information to interviewers. Intentional or unintentional breaking of the blind is to be reported to the PI.

The randomization codes will be kept in a password-protected file accessible to the PI, co-investigators, the project coordinator, and the data manager. When preparing data for analysis, the data manager will

blind code recruitment site and study arm. Masking will be removed for reporting interim results to the DSMB.

In addition, we will adopt a position of clinical equipoise. Intervention facilitators and interviewers will be informed that we are testing two different interventions, but neither is assumed to be superior to the other. Facilitators will be assigned to one or the other, while interviewers will be blinded to participant condition. Data collection will be conducted by interviewers who are not involved in intervention delivery. Interviews will be standardized using a computer-assisted instrument, and sensitive sections will be self-administered.

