9.4 STATISTICAL ANALYSES

9.4.1 GENERAL APPROACH

Descriptive analyses of the study sample will include percentages for categorical variables and means and standard deviations for continuous measures. Chi-square tests and t-tests will be computed to compare study arms on baseline sociodemographic measures. We will compare follow-up between conditions using GEE logistic regression. Results will be reported as odds ratios with 95% confidence intervals and exact p-values for 2-tailed tests.

We will examine the distributions of outcome measures to ascertain whether there is sufficient variability to analyze frequency measures as ordinal. Response categories with a small number of responses will be collapsed for analysis. We will analyze missing data patterns to assess the extent of missing data, and to determine if there is evidence of non-ignorable missingness (i.e. missing not at random, MNAR).

We will conduct repeated measures linear, logistic, and modified Poisson regressions using mixed effects models with random intercepts for subject and recruitment site to test the effect of intervention condition on changes in mediator and outcome variables. In the event of missing data in more than 5% of cases, or unbalanced loss-to-follow-up, analyses will be conducted in Mplus using full-information maximum likelihood methods. We will include the interaction of time and participant type (intervention participant vs. network member) to test for differential effects. Following analysis of the main outcomes we will conduct analyses to explore hypothesized mediation and moderation effects.

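### The interim efficacy analyses are run and reviewed by people who can open the site allocation, and nothing in the plan keeps the blind-code key or the by-arm results from them

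*Combined protocol and SAP*

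**What the plan says.** **Allocation (Section 6.3).** The 12 recruitment sites are matched in pairs, and "randomization will be determined by the PI using a random number generator". The PI then uses the allocation in running the trial: "The PI will inform the Moscow project coordinator of the site assignment as needed for group scheduling". Access is shared: "The randomization codes will be kept in a password-protected file accessible to the PI, co-investigators, the project coordinator, and the data manager".

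**Masking for analysis (Section 6.3).** When preparing data, the data manager will "blind code recruitment site and study arm. Masking will be removed for reporting interim results to the DSMB".

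**Interim analyses (Section 9.4.6).** "Interim analysis of behavioral outcomes will be conducted at each follow-up point". On who does the work: "The analysis will be conducted by the PI with data blind-coded by the data manager". The co-investigators and the DSMB review the output. On its use: "We do not plan to halt the study based on interim results".

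**Related safeguards.** Section 9.1 promises a formal SAP before the first interim analysis. Section 6.3 blinds the interviewers, masks recruitment staff to site assignment and makes sensitive interview sections self-administered. Section 10.1.6 provides an independent DSMB, with biostatistical expertise, that assesses data by arm.

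**The concern.** Blind coding protects when the analyst cannot link the codes to the arms. Here the analyst created the allocation and can look it up, and so can the co-investigators who review the output. The only barrier is the data manager's relabelling, and the plan does not say who keeps that key.

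Two things are at stake. One is conduct: the people directing an 18-month recruitment period and a 12-month follow-up could learn which arm is doing better while self-reported outcomes are still being collected. The other is analysis: some modelling decisions depend on the data, and they could be settled by people who have already seen comparative results. The absence of a stopping rule means no alpha is spent on stopping. It does nothing for either of these.

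**Working it through.** The plan gives no figure on this point to reproduce. The check sets roles against access, then asks how well relabelling would hide the arms.

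**1. Roles and access (Sections 6.3 and 9.4.6)**

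| Role | Can open randomisation file | Part in interim analysis | Blind-code key |
|---|---|---|---|
| PI | Yes, and generates the allocation | Runs it | Not stated |
| Co-investigators | Yes | Review it | Not stated |
| Data manager | Yes | Applies the blind code | Creates it; custody not stated |
| DSMB | Not listed | Reviews it, masking removed | Not applicable |

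No section withholds the key from the PI or co-investigators, suspends their access to the file during analysis, or says who prepares the unmasked DSMB report.

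**2. Number of looks.** Follow-ups are at 3, 6, 9 and 12 months: 4 − 1 = 3 looks before the final time point. Recruitment lasts 18 months (Section 5.5), and the 3-month visit falls at day 125 (Section 1.3). Section 9.4.6 does not say whether a look waits for everyone to reach the visit. If it does not, early sites' results could be seen while later pairs are still being recruited.

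**3. Can the codes be recognised without the key?**
- Sites are recruited two at a time, one per arm (Section 5.5), and the PI receives weekly counts of enrolment, interviews and attendance (governance text before Section 10.1.6). Site sizes and dates are therefore clues to a coded site.
- Section 8.1 asks network members how many MASLIHAT peer educators they know. The plan does not say that such items are removed from the interim file.
- The outcomes themselves may show the arm. This is an illustration, not a figure from the plan. Take the Section 9.2 assumptions: control rate pc of 0.30 to 0.50, MASLIHAT rate pt of 0.05 to 0.15, ICC 0.05, and m = 10 to 30 per site. With k sites per arm, the effective number per arm is n = km / [1 + 0.05(m − 1)]. The chance that the lower-risk coded arm is MASLIHAT is Φ[(pc − pt)/SE], where SE² = [pc(1 − pc) + pt(1 − pt)]/n.

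Worked case, k = 6, m = 10, 0.30 against 0.15: n = 60/1.45 = 41.4; SE = √(0.3375/41.4) = 0.090; z = 0.15/0.090 = 1.66; Φ = 0.95.

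| Sites per arm | Per site | pc, pt | Probability |
|---|---|---|---|
| 6 | 10 | 0.30, 0.15 | 0.95 |
| 6 | 10 | 0.50, 0.10 | >0.999 |
| 6 | 30 | 0.30, 0.15 | 0.987 |
| 1 (first pair only) | 30 | 0.30, 0.15 | 0.82 |
| 1 (first pair only) | 30 | 0.50, 0.10 | 0.99 |

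These values assume that the hoped-for effect is real. With no effect, pc = pt and the formula gives Φ(0) = 0.5, so the outcomes would reveal nothing.

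**4. Which analysis choices remain loose?**
- Collapsing: "Response categories with a small number of responses will be collapsed for analysis", with no number for small (Section 9.4.1).
- Covariates: a rule exists (related to the outcome at baseline, or differing significantly between conditions), but without a numerical threshold (Section 9.4.2).
- Ordinal and binary: Section 9.4.2 plans both. Section 9.4.1 ties ordinal analysis to adequate variability, a property of the distribution and not of the arm difference.
- Stratifying by participant type: a stated trigger, p < .10.

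Only the first two leave real room for judgement.

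**The case against.** A reader might infer that the PI holds the key and takes three unmasked looks. The documents do not support that. Section 6.3 treats the randomisation file and the blind coding as separate. Site is coded as well as arm, so knowing the real allocation does not by itself decode the dataset. Section 9.4.6 says the PI works on coded data, and the only stated unmasking is for the DSMB. What the text shows is missing separation, not planned unmasking.

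A reader might also infer that the whole analysis is open. It is not: several decisions are pre-stated rules, and the SAP due before the first look is the natural place to settle the rest. Nor is the trial unmasked throughout: participants learn their assignment, but interviewers and recruiters are blinded.

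The routes to conduct bias are plausible, not demonstrated. Fidelity feedback comes mainly from session observers, who know the arm from the content (Section 6.2.1). Missed visits follow set contact steps (Section 7.3), and the project coordinator is not listed as receiving interim results. The probabilities above depend on a large true effect and would apply to any coded two-arm comparison with such an effect.

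All of this narrows the point without removing it. Neither the SAP nor the DSMB charter is described as restricting investigator access, and no stated decision requires investigators to see comparative results early.

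**Conclusion.** The point stands as a weakness in role separation that should be corrected. It is not a flaw that invalidates the trial. The PI generates the allocation, the PI and co-investigators can open it, and the same people run or review efficacy results by coded arm at three time points before 12 months. The blind code is the only barrier and it is a weak one.

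The size of any bias cannot be derived from the documents. Under the plan's own expected rates, the coded arms would probably reveal themselves (0.95 or more with all 12 sites in the cases tabulated, 0.82 to 0.99 from one pair). Under no effect the outcomes would not, although site timing and the peer-educator items still could. The conclusion rests on the documents' silence about the key. A SAP or DSMB charter that withheld both the key and the by-arm results from investigators would largely answer it.

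**What to change.** - **Section 9.4.6:** state that by-arm interim results, coded or not, are prepared by the existing data manager and go only to closed DSMB sessions. The PI and co-investigators see only pooled data until the 12-month lock. Pooled should mean without a breakdown by site, because anyone who knows the allocation could rebuild the arm comparison from site results.
- **Section 6.3:** state that the data manager alone holds the blind-code key until lock. Changing 9.4.6 alone would leave custody of the key unstated.
- **SAP:** before any by-arm outcome data are viewed, give the count below which categories are collapsed and how, and the threshold or fixed list for covariates.

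**Cost.** Investigators lose early sight of comparative results, and the data manager takes on the table preparation. No planned decision is affected, since the study continues whatever the interim results show. The data manager belongs to the study team and has file access, so this is not full independence, but it needs no new post.

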9.4.7 SUB-GROUP ANALYSES

The population for the study intervention is homogeneous (Tajik migrant males who inject drugs), therefore we do not plan any sub-group analyses.

9.4.8 TABULATION OF INDIVIDUAL PARTICIPANT DATA

Individual participant data will not be tabulated.

9.4.9 EXPLORATORY ANALYSES

We will conduct analyses to explore hypothesized mediation and moderation effects. We will test whether changes in HIV knowledge, risk awareness, risk reduction self-efficacy, behavioral norms, and social network interactions mediate changes in risk behavior. We will test whether psychosocial well-being (depression, loneliness) moderates intervention effects on risk behavior.

Mediation: We will investigate the effects of intervention condition on theoretical mediators, and test whether changes in proposed mediating variables predict changes in behavior. We will use multilevel structural equation modeling in Mplus to assess mediation effects, with the predictor (intervention condition) at the cluster level (level-2), and mediators and outcomes at the individual level (level-1), using 6-month outcomes and 3-month mediators. This method involves separation of observed variables into latent between and within-cluster components that are modeled separately but simultaneously, producing a theoretically unbiased estimate of the indirect effect.^{76,77}

Peer educator development: We will conduct analyses to test the effects of peer educator training on participant self-esteem, self-efficacy, and substance use self-stigma.

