Interviews: Intervention participants and network members will complete computer-assisted personal interviews (CAPI) at baseline (prior to first intervention session), and at 3, 6, 9, and 12 months post-intervention. All baseline and 12-month interviews will be conducted in a private room at the PRIZMA office; intermediate follow-up interviews may be conducted at the PRIZMA office or at a location selected by the subject. Trained interviewers will administer the 60 to 90-minute questionnaire, using a computer-assisted personal interview (CAPI) system (Qualtrics) to record responses. For the more sensitive questions such as sexual behavior and STIs, the interviewer will instruct the participant to enter his responses. The CAPI system will ensure proper administration of skip sequences. For quality control purposes, 20% of interviews will be randomly selected to be audiotaped, and half of these audiotapes will be reviewed by [name] or [name] for quality assurance. Using electronic data capture and requiring timely data uploads will allow the data manager to monitor research progress and conduct quality control checks. The questionnaires were developed and tested with members of the population using cognitive interviewing (CI).⁶² Translations were validated using "back translation" with a member of the study population.

Self-report Measures

Background measures. The baseline interview includes measures of basic sociodemographic variables (education, marital status, migration history, religion), community involvement/social activities, and health (general health, STIs). The follow-up interviews also collect self-reported STIs since last interview.

Outcome measures. Primary outcome measures are syringe sharing in the past 3 months, and vaginal or anal sex without a condom in the past 3 months. Other measures include syringe cleaning methods, and the Alcohol Use Disorder Identification Test (AUDIT)⁶³ to assess alcohol consumption and alcohol-related problems at each time point.

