Theoretical mediators. In addition to risk behavior, the questionnaire will assess theoretical mediators including HIV knowledge, risk awareness, behavioral norms, self-efficacy, depression, and loneliness. HIV knowledge is assessed with 16 true/false items; risk awareness is assessed with questions such as "How likely are you to get HIV?" and "How much do worry about HIV?" Behavioral norms⁶⁴⁻⁶⁶ will be assessed with questions such as "How many of your friends who shoot drugs use a needle after someone else, without bleaching or cleaning?" (descriptive norms), and "How many of your friends would disapprove if you shared a needle with a stranger?" (injunctive norms). Responses are given on a 5-point scale from 1 (none) to 5 (all). Self-efficacy for safer drug injection will be measured with six items adapted from the CIDUS-III study⁶⁷ (e.g., "I can avoid sharing a needle even if I am dope sick or in withdrawal"), rated on a four-point scale from "strongly agree" to "strongly disagree". Depression will be measured using the Centers for Epidemiological Studies Depression Scale -- Revised (CESD-R)⁶⁸, and loneliness will be measured using the UCLA Loneliness Scale⁶⁹.

Network penetration & diffusion. Diffusion of MASLIHAT messaging/norms at the network level will be assessed using measures successfully used by SHIELD and other public opinion leadership interventions such as asking network members as to how many (if any) MASLIHAT peer educators they know, whether anyone within their drug using network talked with them about HIV since they were last interviewed, and whether they talked about specific topics (e.g. condom use, syringe cleaning, HIV testing).

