9.4.2 ANALYSIS OF THE PRIMARY ENDPOINT(S)

Relative frequency of syringe sharing, equipment sharing, and vaginal or anal sex without a condom in the past 3 months will be measured at each time point on a 7-point Likert-type scale (Never, Rarely, Less than half the time, About half the time, More than half the time, Most of the time, Always). We will analyze ordinal outcomes, and we will also dichotomize responses to analyze binary (none/any) outcomes.

We will conduct repeated measures mixed effects regressions with random intercepts for subject and recruitment site to test the effect of intervention condition on changes in the outcome variables. We will use ordinal logistic regression for ordinal outcomes and modified Poisson regression for binary outcomes. We will conduct a test of the proportional odds assumption with a likelihood ratio test comparing the proportional odds model with a non-proportional odds model.⁷⁴ We will include the interaction of time and participant type (intervention participant vs. network member) to test for differential effects. If the interaction term suggests differential effects ($p < .10$), we will stratify analyses by participant type. Sociodemographic characteristics (age, education, time in Moscow) will be included as covariates in the analysis if they are related to the outcome at baseline or if they vary significantly across conditions. All participants with at least one follow-up interview will be included in the analysis.

Dosage: If there is variability in attendance, we will estimate repeated measures mixed effect models predicting outcomes with session attendance and the interaction between time, intervention condition, and session attendance as predictors. A significant interaction effect will indicate that the effect of the intervention is moderated by session attendance.

Social Network Diffusion. Additional analyses among network members will examine associations between exposure to intervention concepts (i.e. conversations about health, drugs/alcohol HIV) and changes in outcomes over time.

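### The mediation model in 9.4.9 names no baseline adjustment, so the mediator-to-behaviour path is open to confounding by persistent baseline differences

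*Combined protocol and SAP*

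**What the plan says.** Section 9.4.9 (Mediation) plans to "test whether changes in proposed mediating variables predict changes in behavior". The model is a multilevel SEM with arm at site level and mediators and outcomes at individual level, "using 6-month outcomes and 3-month mediators". The section says that splitting variables into between-site and within-site components has the effect of "producing a theoretically unbiased estimate of the indirect effect". It names no baseline value, change score or covariate.

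Other sections do not supply them for this path:

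- Section 9.4.1 plans repeated-measures models for the effect of arm on change in mediators and outcomes. These do not model the effect of a mediator on behaviour.
- Section 9.4.2 has a covariate rule for the primary analysis: "Sociodemographic characteristics (age, education, time in Moscow) will be included as covariates in the analysis", subject to conditions. It includes no baseline mediator or outcome.
- Section 9.1 promises a formal SAP before the first 3-month analysis. It is not among the documents.

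The data needed are collected. Section 8.1 states that "Intervention participants and network members will complete computer-assisted personal interviews (CAPI) at baseline", before the first session, and that "the questionnaire will assess theoretical mediators including HIV knowledge, risk awareness, behavioral norms, self-efficacy, depression, and loneliness". The objectives table in Section 3 lists mediation under tertiary/exploratory.

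**The concern.** The stated question is whether a change in the mediator goes with a change in behaviour. A model that holds only a 3-month mediator and a 6-month outcome tests something else: whether the level of one predicts the later level of the other. Men with safer norms or higher self-efficacy at entry plausibly already shared less. If both characteristics persist, the levels are associated at follow-up whatever the intervention did to the mediator.

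Randomisation does not help here, because nobody is randomised to a level of the mediator. The between/within split does not help either. It stops site-level and individual-level associations from being mixed, but it leaves confounding in place at each level. At stake is the account of how MASLIHAT works, which Section 4.1 states as a hypothesis: an inert mediator could be described as driving behaviour.

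**Working it through.** The plan gives no power or error rate for the mediation analysis, so there is no figure to reproduce. The check asks how often the mediator-to-outcome slope is declared significant when its true value is zero.

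**Inputs from the documents.** 12 sites, 6 per arm (6.3); 30 men per site for the complete sample and intracluster correlation 0.05 (9.2).

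**Assumed, because the documents are silent.** Baseline mediator-outcome correlation r = 0.3 (shown as a magnitude; the sign sets only the direction of the bias); unit variances; two-sided 5% test; arm effect on the mediator 0.8 SD. Persistence is modelled in two ways: carry-over with stability s, or stable traits measured with reliability 0.7.

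**Within-site slope, follow-up values only.**

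- Carry-over: each follow-up value is s times its baseline plus independent error, so the slope is b = s² × r.
- Stable trait: b = 0.7 × 0.95 × r / (0.7 × 0.95 + 0.3), where 0.95 is the within-site share. For r = 0.3 this is 0.1995 / 0.965 = 0.207.
- Standard error: √[(1 − b²)/347], with 360 men − 12 site means − 1 slope = 347. The rejection rate follows from z = b/SE against 1.96.

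| Persistence (r = 0.3) | b | SE | z | Rejection by formula | By simulation |
|---|---|---|---|---|---|
| Carry-over, s = 0.3 | 0.027 | 0.0537 | 0.50 | 8% | 7% |
| Carry-over, s = 0.5 | 0.075 | 0.0535 | 1.40 | 29% | 29% |
| Carry-over, s = 0.6 | 0.108 | 0.0534 | 2.02 | 52% | 52% |
| Carry-over, s = 0.7 | 0.147 | 0.0531 | 2.77 | 79% | 80% |
| Stable trait | 0.207 | 0.0525 | 3.94 | 98% | 98% |

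For a binary outcome, simulated rejection at r = 0.3 is lower: 5 to 47% under carry-over and 23 to 75% under stable traits.

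**Between-site indirect effect.** Arm is a site-level variable, so the indirect effect is formed from site means. In the stable-trait simulation at r = 0.3 the between-site slope has median 0.25 in magnitude, so the spurious indirect effect is 0.8 × 0.25 = 0.20 SD. Carry-over gives less: at s = 0.5, 0.8 × 0.075 = 0.06 SD. Across settings at r = 0.3 the shift is roughly 0.01 to 0.2 SD, or about 1 to 6 percentage points for a binary outcome. The site-level mediator-to-outcome test rejects only about 4 to 12% of the time, because 12 sites give it little power.

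**With baseline mediator and baseline outcome as covariates.** Within-site rejection is 4 to 6% under carry-over. Under stable traits with reliability 0.7 it is 10% at r = 0.3 and 30% at r = 0.5, against 98% and 100% without them.

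**Change scores instead.** Under stable traits these give about 5%. Under carry-over they do not: b = (1 − s) × r / 2, which is 0.7 × 0.3 / 2 = 0.105 at s = 0.3 and 0.3 × 0.3 / 2 = 0.045 at s = 0.7. With SE about 0.053 these give z of about 1.97 and 0.84, or rejection of about 50% and 13%. Simulation gives 13 to 52%.

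**Degrees of freedom between sites.** Intercept, arm and mediator leave 12 − 3 = 9. Adding both baseline site means leaves 12 − 5 = 7.

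**The case against.** The strongest reply is that the plan never says its variables are raw, unadjusted levels. It speaks of change, and the months may only fix the time order. That is fair: the text is silent, and the later SAP could fill the gap. But no section says how change enters this model, and the working shows that the choice between change scores and baseline covariates matters.

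The second reply is that the large rejection rates belong to the within-site slope, which is not part of the indirect effect of a site-level intervention. This stands. A reader might infer that inert mediators will often be declared significant mediators; with 12 sites that does not follow. What remains is a shifted indirect estimate and a within-site slope that is easily read as evidence that change predicts change.

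Third, the outcomes are ordinal or binary, and the pilot results in 9.2 are near the floor at six months (syringe sharing 52% to 0%, condomless sex 35% to 1%). With 45% assumed in controls and 1 to 5% under MASLIHAT, simulated within-site rejection is 14 to 42% and the indirect shift is about 1 to 3 percentage points, against a total effect of 40 to 44. The problem shrinks but does not vanish.

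Fourth, the unbiasedness wording is tied to the between/within separation and cites methods papers, so it need not be a claim of no confounding. Even so, a reader could take it as one.

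**Conclusion.** The point holds in a limited form. As specified, the model in 9.4.9 leaves the mediator-to-behaviour path open to confounding by persistent baseline differences, and the separation of levels does not remove it. The direction is clear whenever the baseline correlation is not zero and both variables persist. The size is not known, because the documents give neither quantity: the within-site error can be close to nominal or very large.

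Three stronger readings are not supported. The documents do not state that baseline values are to be left out. The significance test of the indirect effect is not badly inflated. No primary or secondary conclusion depends on this analysis. It is a worthwhile correction to an exploratory analysis, not a threat to the trial's main results.

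**What to change.** In 9.4.9, or in the formal SAP:

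1. Add the baseline mediator and the baseline outcome as individual-level covariates in both the mediator and the outcome equation, keeping the 3-month and 6-month follow-up values. Do this wherever a baseline value exists: HIV knowledge, risk awareness, norms, self-efficacy and the risk behaviours. Conversations arising after the intervention, part of the social-network-interaction mediator, have no meaningful baseline, and the plan should say so.
2. Enter the baseline values at site level only as a sensitivity analysis, because of the loss of degrees of freedom.
3. State that the indirect effect is unbiased only if no mediator-outcome confounding remains, and that unreliable baseline measures leave some.

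The cost is SAP wording and two covariates per equation. No new data, visits or participants are needed.
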